Cover Page Study Protocol

Date: 4/28/2022

All the information contained in this document including the Study Protocol and Statistical Analysis Plan are directly related to the study entitled:

Effects of Physical Therapy on Isometric Neck Retraction Strength and Pain in Patients with Neck Disability

NCT04334655

The primary researcher [name] changed positions from Campbell University to The University of Tennessee at Chattanooga in August 2020. Campbell University provided oversight of this project until August 14th, 2020 and after August 14th 2020 the study was covered under the IRB of The University of Tennessee at Chattanooga (IRB # 20-082). Other than changing the name on the top of the consent form from Campbell University to The University of Tennessee at Chattanooga, no other changes were made to the methods or procedures.

Study Protocol

Four physical therapists (PT) from four different outpatient clinics will collect demographic, anthropomorphic, and isometric neck retraction strength data with an Hand Held Dynamometer (HHD) in patients with primary complaints of neck pain at the time of the initial evaluation, regular follow-ups, and at discharge. The PT will also include a shortlist of the primary interventions used during the course of treatment. A short video explaining how to test isometric neck retraction strength will be provided to each clinic and the description can also be found in the investigator's previous article entitled "Reliability and validity of measurements of cervical retraction strength obtained with a hand-held dynamometer." Basically, the patient will lay on their back with the HHD under the external occipital protuberance. The patient will then perform a practice isometric contraction at 50% maximum force followed by two maximum effort trials with 1-minute in-between.

A follow-up phone call will be made to each clinic to assure that the units arrived and to answer any additional questions regarding the procedure or data to be collected. Follow up phone calls will then be performed monthly to assess progress. At the end of three months, a preliminary analysis, based on the total number of documented patients will be made. A power analysis indicates that 40 patients will be sufficient to answer our research question. This is based on a 2007 article by Cagnie, B. in the Archives of Physical Medicine Rehabilitation entitled "Differences in isometric neck muscle strength between healthy controls and women with chronic neck pain: the use of a reliable measurement." To account for drop-outs the investigators raised this to an n=60.

Data will be collected over a secure Qualtrics server to which each participating PT will have an individual access code. No identifiable patient information will be given to the investigators. Data analysis will include Pearson or Spearman correlation coefficients to examine the relationship between isometric neck strength with patient-reported outcome measures including the Numeric Pain Rating Scale (NPRS) and Neck Disability Index (NDI). Repeat Measure ANOVA will be used to compare the variables including strength over different time frames throughout the episode of care. An intention to treat analysis will be used for patients who do not complete the study or their Physical Therapy (PT) care.

Data will be collected on 60 consecutive patients with neck pain. Inclusion criteria include patients over the age of 18 years that are receiving physical therapy with

primary complaints of neck pain. Exclusion criteria include individuals with a history of cervical neck surgery as well as those with neurologic diseases or Chronic Obstructive Pulmonary Disease (COPD).

Day 1: Patient with a primary complaint of neck pain is seen in one of the four physical therapy clinics participating in the study. The patient is recruited by the PT in the clinic. The study will be explained to the patient and written consent obtained and filed in the clinic. A copy of the consent will also be given to the participant.

The PT conducts their initial evaluation and treatment as they normally would with the addition of a test for isometric neck strength. Measuring neck strength is a normal procedure for a PT to perform and is well within the scope of practice for physical therapists. Many clinics do not have hand-held dynamometers (HHD) so we will be providing the dynamometers and mailing them to each clinic. The MicroFET2 hand-held dynamometer is FDA approved (Regulation number: 21 CFR 888.1240) and will be used only in the manner for which it was attended, i.e. to measure isometric strength. The hand-held dynamometer is placed in a cradle behind the patient's head in supine. Instructions are given to retract the chin and head into the dynamometer three times. 1 practice trial at 50% and 2 maximum effort trials with 1 minute between attempts. This is outlined in the investigator's 2019 study (Reliability and validity of measurements of cervical retraction strength obtained with a hand-held dynamometer. Journal of Manual and Manipulative Therapy. 2019;27(4): 222-228.) The entire procedure will take approximately 5 minutes. This information is recorded along with anthropomorphic data, pain levels, neck disability index, and treatment performed. All information is coded and sent to the primary researchers over a secure Qualtrics connection.

4. The patient will receive regular Physical Therapy care. The neck strength, pain, and neck disability index are recorded at re-assessments (usually monthly) and at discharge. The use of this assessment will in no way impact the quality or quantity of PT received by the patient

Statistical Analysis Plan (SAP)

The primary measure of interest in this study is neck retraction force. The average of 2 trials will be used in all strength analysis. Secondary measures such as the Numerical Pain Rating Scale and the Neck Disability Index will be used to characterize the neck pain. Paired t-tests and standardized response mean will be used to describe the responsiveness of neck retraction forces in patients receiving therapy for neck pain. Convergent validity will be examined by calculating spearman correlations between baseline neck retraction force, numerical pain rating scale scores, and neck disability index scores (expressed as percentages).

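### The plan promises intention-to-treat for non-completers, but the analyses it names for change in neck retraction force leave them out

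*Combined protocol and SAP*

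**What the plan says.** The SAP section sets the outcome: "The primary measure of interest in this study is neck retraction force". For its change over time the document names two analyses.

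- Study Protocol, data analysis paragraph: "Repeat Measure ANOVA will be used to compare the variables including strength over different time frames throughout the episode of care".
- SAP section: "Paired t-tests and standardized response mean will be used to describe the responsiveness of neck retraction forces".

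On patients who stop early there is one sentence, in the protocol's data analysis paragraph: "An intention to treat analysis will be used for patients who do not complete the study or their Physical Therapy (PT) care". It gives no imputation rule, no model, and no rule for a patient without a discharge value. The SAP section does not mention missing data.

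Measurements are taken "at the time of the initial evaluation, regular follow-ups, and at discharge" (Study Protocol, opening paragraph). Item 4 adds: "The neck strength, pain, and neck disability index are recorded at re-assessments (usually monthly) and at discharge". The number and timing of re-assessments are therefore not fixed per patient.

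On sample size: "A power analysis indicates that 40 patients will be sufficient to answer our research question", and then "To account for drop-outs the investigators raised this to an n=60".

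**The concern.** In a single-arm cohort, intention-to-treat can only mean that every enrolled patient stays in the analysis of change. The methods named do not do that. A paired t-test and an SRM need both values of the pair. A classical repeated-measures ANOVA needs every visit in the model, so it loses the non-completers and also any patient discharged before a re-assessment that enters the model.

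What is at stake is the main estimate, the size of the change in force and its SRM, more than a p-value. If patients who are doing poorly stop more often, an analysis of those who reach discharge overstates the improvement. The promise of intention-to-treat would lead a reader to think that this had been dealt with.

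**Working it through.** **Step 1: who enters each named analysis.**

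| Patient | Paired t-test and SRM, initial to discharge | Classical repeated-measures ANOVA including a re-assessment |
|---|---|---|
| All visits recorded | in | in |
| Discharged before any re-assessment | in | out |
| Stopped after a re-assessment, no discharge value | out | out |
| Initial value only | out | out |

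If only initial evaluation and discharge enter the ANOVA, it is the same test as the paired t-test (F = t squared), so it does not recover the non-completers either.

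**Step 2: how many patients the plan allows for.** The 40 cannot be reproduced, because no alpha, power, effect size, SD or test is stated. The step to 60 can be back-solved: 40/(1 − d) = 60 gives d = 1 − 40/60 = 33.3%, or 20 of 60. The documents state no drop-out rate, so 20 is the most that can be lost while still keeping 40.

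**Step 3: does the missing method matter?** Take one third of patients as non-completers. As an illustration only, give each of them zero change (initial value carried forward). With a completer SRM of s (SD of change 1), the all-patient mean is (2/3)s and the variance is (2/3)(1 + s²) − ((2/3)s)². For s = 0.60: mean 0.40, variance 0.907 − 0.160 = 0.747, SRM 0.40/0.864 = 0.46. In the same way 0.40 becomes 0.32 and 0.80 becomes 0.59. The label intention-to-treat covers all of these results.

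**Step 4: size of the completer bias.** From the documents: 60 enrolled, 40 completers on average. Assumed, and not in the documents: three visits; true change 0.50 in SDs of change, half of it reached by the middle visit; every drop-out is seen at the middle visit; the odds of drop-out rise by a factor of 1, 2 or 3 per SD of poorer interim change; correlation between visits either equal at 0.7 or first-order autoregressive at 0.7. Simulated mean estimates (excess = completers/0.50 − 1):

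| Correlation | Odds ratio | Completers | Excess | Random-intercept model, all 60 |
|---|---|---|---|---|
| Equal 0.7 | 1 | 0.501 | none | 0.502 |
| Equal 0.7 | 2 | 0.611 | 22% | 0.504 |
| Equal 0.7 | 3 | 0.651 | 30% | 0.502 |
| Autoregressive 0.7 | 1 | 0.499 | none | 0.499 |
| Autoregressive 0.7 | 2 | 0.645 | 29% | 0.565 |
| Autoregressive 0.7 | 3 | 0.697 | 39% | 0.582 |

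In the two autoregressive rows with selective drop-out, a likelihood fit with unstructured covariance gives 0.500 and 0.499. Drop-out there depends only on observed values, so missing at random holds. What remains in the random-intercept column comes from forcing equal correlations.

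**Step 5: sensitivity.** If half of the drop-outs leave at random before the middle visit, completers show 0.566 to 0.623 at odds ratios 2 to 3, which is 13% to 25% too large. If the change and the odds ratio are both expressed in baseline SDs instead, completers under equal correlation show about 0.54 to 0.60, which is 8% to 20% too large.

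**The case against.** **The intention-to-treat sentence already covers these patients.** It shows the right aim, and an analyst could meet it by imputation. But no method is given, and step 3 shows that the choice moves the SRM materially. Neither named test carries a method of its own.

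**Nothing in the documents says that poor responders leave.** This stands. The drop-out mechanism, odds ratios, number of visits and correlations are all assumed. Under random drop-out the completer estimate is unbiased and only precision is lost. A reader might also infer that a third of patients will be missing; the documents give an allowance, not a forecast.

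**Two tests for one outcome are a contradiction between protocol and SAP.** A reader might infer this from the ANOVA in one section and the t-tests in the other. The documents do not support it. The two can coexist, one for the time course and one for responsiveness, and the SAP section is naturally read as governing. The analysis sentences do leave out their visits, but the collection times are stated elsewhere, and initial evaluation to discharge is the obvious pair. On its own that would be missing detail.

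**The study is small and descriptive.** This is true, and it limits the weight of any p-value. It does not protect the SRM, which is the descriptive result itself and is computed from completers.

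**Conclusion.** The point holds as a mismatch between a stated aim and the methods named to meet it. The plan promises intention-to-treat for non-completers, while its paired t-tests, SRM and repeated-measures ANOVA in their classical form exclude them. That rests on the text alone.

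The size is conditional. Up to 20 of 60 patients could be omitted within the plan's own allowance. With selective drop-out as assumed in step 4, the completer change is 22% to 39% too large; the milder assumptions of step 5 give 8% to 25%; unrelated drop-out gives none. The documents do not show that such bias will occur, so it should not be reported as a finding about the results. The change is worth making because it is cheap and lets the plan do what it says.

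**What to change.** In the Study Protocol, replace the repeated-measures ANOVA sentence with a likelihood-based mixed model for repeated measures on all recorded visits of all enrolled patients. Fixed effects: visit category (initial evaluation, re-assessment, discharge) and clinic. Covariance: unstructured across visit categories, with a simpler structure only if that fails to converge; a random intercept alone is not enough (step 4). Say how several re-assessments in one patient are handled, for example numbered in order. State that this model is the intention-to-treat analysis of change from initial evaluation to discharge.

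In the SAP section, keep the paired t-test and SRM as the responsiveness analysis, from initial evaluation to discharge with 95% confidence intervals, and label it a completer analysis. Report both estimates side by side, with the number of patients in each and the number who have only an initial value.

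Cost: wording in two sections and modest extra analysis, with no new data. Visit category is used because the documents do not say whether visit dates are captured. The limits should be stated: the model relies on missing at random and on a suitable covariance, and patients with only an initial value add little information on change. The cover page shows that the study was under way by August 2020, so if data have already been examined, the change should be dated and described as such.

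### The repeated-measures ANOVA treats clinic-driven occasions of unequal elapsed time as the same level, and in classical form drops patients who finish care early; force should be modelled on days since baseline

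*Combined protocol and SAP*

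**What the plan says.** The opening of the Study Protocol has force collected "at the time of the initial evaluation, regular follow-ups, and at discharge". Step 4 adds: "The neck strength, pain, and neck disability index are recorded at re-assessments (usually monthly) and at discharge". The length of care is left to practice: "The patient will receive regular Physical Therapy care". Neither part of the document gives a follow-up date, a window, a minimum or maximum episode, a criterion for discharge, or a measurement after discharge.

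The longitudinal analysis appears in the protocol's data-analysis paragraph: "Repeat Measure ANOVA will be used to compare the variables including strength over different time frames throughout the episode of care". The time frames are not defined. The SAP does not repeat the ANOVA. For force, the primary measure, it says: "Paired t-tests and standardized response mean will be used to describe the responsiveness of neck retraction forces in patients receiving therapy for neck pain". It does not name the two occasions that form the pair.

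The only text on incomplete follow-up is: "An intention to treat analysis will be used for patients who do not complete the study or their Physical Therapy (PT) care". No method is attached to it.

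**The concern.** An occasion in this study is an event in a course of care and has no fixed time. A patient discharged at week 3 may have only a baseline and a discharge value. A patient in care for four months may have a baseline, three re-assessments and a discharge value. Both have finished care, and neither is a drop-out.

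Two consequences follow from the text alone. First, a factor level such as discharge, or a given re-assessment, combines different elapsed times. Second, because nothing is measured after discharge, a second or later re-assessment can contain only patients still in care. A classical repeated-measures ANOVA needs a value at every level, so it either loses the early finishers or leaves the levels to be chosen once the data are seen.

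At stake is the meaning of the strength trajectory over the episode of care and, if the unnamed SRM pair is baseline to discharge, of the responsiveness statistic for the primary measure. The SRM would then partly reflect how long patients are kept in care.

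**Working it through.** **1. The plan's own figure.** The sample size is the only number available: "A power analysis indicates that 40 patients will be sufficient to answer our research question" and "To account for drop-outs the investigators raised this to an n=60". The 40 cannot be reproduced, because the documents give no alpha, power, effect size, SD or test. The second step can be solved backwards: 40/(1 − d) = 60 gives d = 1 − 40/60 = 33.3%. The increase therefore covers a loss of one third. It is described as an allowance for drop-outs, and patients who finish care early are not drop-outs. This point changes neither figure.

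**2. How many patients reach a later re-assessment.** The monthly discharge probability h is an assumption, because the documents give no episode length. The number in care after month k is 60 × (1 − h)^k.

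| h | month 1 | month 2 | month 3 |
|---|---|---|---|
| 30% | 42 | 29 | 21 |
| 50% | 30 | 15 | 8 |
| 70% | 18 | 5 | 2 |

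Keeping 40 complete cases out of 60, with no drop-out at all, needs (1 − h)^k ≥ 2/3. That means h ≤ 33.3% for one re-assessment and h ≤ 1 − √(2/3) = 18.4% for two.

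**3. Whether those patients are representative.** All inputs here are assumptions. Recovery rate is lognormal (median 0.5 per month, log SD 0.5), and discharge occurs when cumulative recovery reaches 1, limited to 0.5 to 6 months. The median time to discharge is then 2 months (10th to 90th percentile about 1.1 to 3.8). Force gain per month has mean 0.50 and SD 0.50 between patients, in units of the error SD of change. The correlation between log recovery rate and force gain is r.

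A patient is in care beyond 2 months when the recovery rate is below its median. The mean gain among them is 0.50 − 0.50 × r × √(2/π) = 0.50 − 0.399r. Simulation of 400,000 patients per value of r agrees.

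| r | gain per month, in care beyond 2 months | shortfall from 0.50 | SRM, baseline to discharge |
|---|---|---|---|
| 0 | 0.50 | none | 0.66 |
| 0.3 | 0.38 | 24% | 0.61 |
| 0.5 | 0.30 | 40% | 0.57 |
| 0.7 | 0.22 | 56% | 0.51 |

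A complete-case ANOVA with levels at baseline, month 1 and month 2 uses these same patients throughout. It would show gains of 0.38 then 0.76 at r = 0.3, or 0.22 then 0.44 at r = 0.7. Each is a straight line with too low a slope.

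**4. The SRM at like durations.** At a common time t the SRM is 0.50t/√((0.50t)² + 1). At 2 months, the median episode, this is 1.0/√2 = 0.71. The discharge SRM of 0.66 to 0.51 should be set against that value. The 1-month SRM is 0.5/√1.25 = 0.45, and most of its distance from the discharge figures is extra time in care. Even at r = 0, with the same rate of gain, halving every episode moves the discharge SRM from 0.66 to 0.46. Duration therefore affects the statistic without any selection.

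**The case against.** The strongest objection is that no discharge criterion is given. A reader might infer that patients are discharged when they recover, so that later occasions must over-represent slow responders. That is plausible, but it is not in the documents, and at r = 0 the later re-assessments lose patients without this bias. The direction and size of any bias are therefore conditional. This part of the objection stands.

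A reader might also infer that every later occasion is selected, or that the trajectory would show a false plateau. Neither is supported. Every patient who completes care reaches the discharge occasion. In the complete-case calculation above the slope is lowered but the line does not flatten. A plateau would need means taken from different sets of patients to be compared, and the plan does not say it will do this.

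The ANOVA levels are also undefined. If they turn out to be initial evaluation and discharge only, no completer is dropped and only the unequal durations remain. Whole-episode change is, moreover, a natural summary for an observational study of usual care, and the SAP uses the SRM descriptively. An SRM at a common week answers a different question and should not replace it. Finally, the data-collection form is not reproduced, so dates may already be captured.

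What remains is that elapsed time is neither stated as recorded nor used in any planned analysis, the time frames and the SRM pair are unnamed, and the intention-to-treat sentence does not reach patients who finished care early.

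**Conclusion.** The concern holds as a gap in the longitudinal analysis that should be closed. Two parts rest on the text alone: unequal elapsed times share a level, and successive re-assessments can hold only patients still in care. The loss of early finishers follows if the ANOVA is run in its classical form with one or more re-assessment levels.

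The size rests on assumptions. With 30% to 70% discharged each month, 29 to 5 of 60 patients would remain after month 2. The monthly gain estimated from patients in care beyond 2 months would be unbiased if discharge is unrelated to recovery, and 24% to 56% too low at assumed correlations of 0.3 to 0.7. The documents do not show which of these applies, so bias towards slow responders should not be reported as established. For the SRM, the unequal durations matter in either case if the pair is baseline to discharge, but the re-assessment selection does not apply to it.

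**What to change.** Record days since Day 1 at every assessment, which keeps the data de-identified. If collection has ended, recover them from the form submission dates where possible.

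Replace the repeated-measures ANOVA with a mixed model for force on elapsed time since baseline, using all patients and all their assessments, discharge values included. State in the SAP that baseline to discharge is the pair for the paired t-test and SRM, and report the distribution of episode length beside it. Do not interpret means at late re-assessments that few patients reach. An SRM at a common elapsed time, about week 4, may be added as secondary; it captures less than the whole-episode change.

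The cost is one form field, SAP wording and slightly more analysis work; care and visits do not change. The model assumes that missing later values are explained by the observed data. If discharge depends on something that is not recorded, it keeps the early finishers in the estimate but need not remove all of the bias, and the SAP should say so.
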